UPPS-P Impulsive Behavior Scale-59 item questionnaire assesses 5 facets of impulsivity including sensation seeking, lack of premeditation, lack of perseverance, negative urgency, and positive urgency. - 20min

Behavioral Tests

Monetary Choice Questionnaire (delay discounting) 27-item assessment requiring subjects to select choices between larger-later sums of money available with a delay or smaller-sooner sums of money available immediately.-5min

(1b) Beads Task:Computerized task where subjects are presented with up to 20 drawn beads from two jars and asked to infer from which jar the beads were drawn. Following their decision, they indicate their degree of confidence that their answer is correct without feedback.-5min

(2) Motor/Action Impulsivity- (2a) 4-Choice Serial Reaction Time task (4-CSRTT): The 4-CSRTT is the human analog computerized task based on the rodent 5-CSRTT to assess premature responding. When four boxes appear on the screen, subjects hold down the space bar, indicating the cue onset time. After a specified time, a green circle target appears briefly and randomly in one of the four boxes. Subjects release the space bar and touch the box in which the target appeared. Premature responding is defined as early release of the space bar before target onset- 5min

(2b) Stop Signal Task assesses response inhibition. A series of go stimuli in the form of left or right arrows are presented and subjects are instructed to respond as quickly as possible by pressing the respective button. The key outcome is the stop signal reaction time (SSRT).-5min

Please attach copies, unless standard instruments are used

Off label and investigational use of drugs/devices

Choose from the following that will be applicable to your study

✓ Drug

Select the number of drugs used in this study

2

Drug #1

Name of the drug

Lorcaserin

Manufacturer and other information

Name of the drug

Lorcaserin (Belviq)

Manufacturer and other information

Lorcaserin (Belviq) is a weight-loss drug developed by Arena Pharmaceuticals. It has serotonergic properties and acts as an anorexiant.

An example of study medication label will appear as follows:

Protocol #

Participant ID: 001-ABC

Study Week: #2

Lorcaserin 10mg tablet

Directions for use: Take 1 tablet by mouth once

Dispense: 1 tablet

Caution: New Drug-- Limited by Federal (or United States) law to investigational use

Approval Status

IND is approved

IND#

129105

Who holds the IND/IND sponsor?

Other

Enter Name

[name]

Drug #2

Name of the drug

Lorcaserin XR

Manufacturer and other information

Lorcaserin XR (BelviqXR)

Manufacturer and other information

Lorcaserin XR (Belviq XR) is a weight-loss drug developed by Arena Pharmaceuticals. It has serotonergic properties and acts as an anorexiant.

An example of study medication label will appear as follows:

Protocol #

Participant ID: 001-ABC

Study Week: #3

Lorcaserin XR 20mg tablet

Directions for use: Take 1 tablet by mouth daily.

Dispense: 7 tablets

Caution: New Drug-- Limited by Federal (or United States) law to investigational use

Approval Status

IND is approved

IND#

129105

Who holds the IND/IND sponsor?

Other

Enter Name

[name]

Research Related Delay to Treatment

Will research procedures result in a delay to treatment?

No

Treatment to be provided at the end of the study

Upon study completion or at the point of dropout, participants will be provided with referrals to community practitioners and offered the option of continued medical management counseling, focused on goals for abstinence and utilization of additional resources in the community for up to four weeks following the end of the study.

Clinical Treatment Alternatives

Clinical treatment alternatives

Unfortunately, there are no FDA-approved medications for the treatment of cannabis use disorder. Several psychotherapy methods have been shown to be effective in treating cannabis use disorder and include: Relapse Prevention Therapy, a form of CBT; Contingency Management, a prize- or voucher-based incentive treatment; Motivational Enhancement Therapy (MET), a form of Motivational Interviewing; the combination of CBT and MET together; and family therapy. However, success rates for psychotherapies have been modest (less than 50%). During the study, participants are permitted to seek additional help from other providers (therapists and physicians outside of the study). Patients are informed that they may request referral for other treatment options.

Risks/Discomforts/Inconveniences

Risks that could be encountered during the study period

Study Medication Risks: One of the main risks associated with participation is drug administration.

Lorcaserin XR (or Bleviq XR[®]) was approved by the FDA for treating obesity, is generally well tolerated, and has low abuse potential. The target daily dose of lorcaserin in the proposed study (20mg) is the current FDA approved dose for the treatment of weight management. In clinical trials, headache was the only reported side effect to occur at a frequency much greater than placebo. Other possible side effects of lorcaserin include: constipation, dry mouth, headache, nausea, and dizziness. Some rare but serious side effects include hypoglycemia in patients with Type 2 diabetes, serotonin syndrome, agitation, confusion, hallucinations, arrhythmias, cardiac valve disease, depression, thoughts of suicide, and an erection lasting longer than 4 hours.

The combination of lorcaserin with other serotonergic medications (e.g., 5HT₃ antagonist antiemetics, bupropion, triptans, SSRIs, SNRIs, TCAs, St. John's Wort, tryptophan), medications that impair the metabolism of serotonin (e.g., MAO inhibitors, dextromethorphan, tramadol, lithium), or antidopaminergic medications (e.g., antipsychotics) may enhance serotonergic effects, and this could result in rare but serious serotonin syndrome reaction. Signs of serotonin syndrome include: mental status changes (e.g., anxiety, agitated delirium, restlessness, and disorientation); easy startle, autonomic manifestations (e.g., diaphoresis, tachycardia, hyperthermia, hypertension, vomiting, and diarrhea); and neuromuscular hyperactivity (e.g., tremor, muscle rigidity, myoclonus, hyperreflexia, and bilateral Babinski sign).

The combination of lorcaserin with ergot derivatives is contraindicated. The use of these drugs together may increase the risk of developing valvular heart disease in addition to enhancing serotonergic effects that may result in serotonin syndrome.

The combination of lorcaserin with 5HT_{2B}-R agonists (e.g., cabergoline) is contraindicated due to the increased risk of cardiac valvulopathy.

Lorcaserin is a moderate CYP2D6 inhibitor and may decrease the clearance of drugs metabolized by CYP2D6, and thus raise these other drug levels increasing the risk of toxicity.

Lorcaserin is contraindicated in pregnancy due to the fact that weight loss offers no clinical benefit in pregnancy and is advised against.

Other Risks: Blood draws may cause slight discomfort at the site of needle entry, can result in infection at the site if hygienic/sterile techniques aren't used, or can result in a small bruise.

Participants will receive compensation and incentives during the study that could pose a risk of providing more available funds to purchase cannabis.

The structured interviews, rating scales, and questionnaires should add no physical risk. The major disadvantage is the time required to complete them and that some of the questions might be embarrassing to participants. Our past experience with these measures indicates that they are acceptable to participants. However, some people have found them uncomfortable and/or tiring because the interviews/assessments are long and of a personal nature.

Describe procedures for minimizing risks

1) Screening Procedures

In order to minimize the risk associated with the study, subjects undergo a comprehensive medical and psychiatric evaluation during the screening procedure. The baseline medical evaluation consists of a physical examination, blood chemistry profile, complete blood count, urinalysis, serum pregnancy test, urine toxicology and is designed, along with the clinical history, to detect chronic and/or unstable medical illnesses. A comprehensive psychiatric assessment is performed during the screening process, and is intended to detect and assess all past and current psychiatric disorders. The eligibility criteria (see above) are designed to minimize the medical and psychiatric risks to participants by excluding those for whom participation would place them at an increased risk. Special attention will be given to patient's concurrent

use of medications. Participants on medications that meet exclusion criteria will not be included in the study. If participants have recently completed another study at STARS, we will ensure, as with other medications, that there are no drug-drug interactions with the possible recent exposure to other study medications or will ensure proper time for wash-out between studies.

2) Study Procedures

Participants will be informed about the possible side effects and risks (listed above) of taking lorcaserin both alone and in combination with other medications through extensive discussions with staff psychiatrist(s) during the consent process. Participants will be told to contact the clinic if they experience any adverse effects and given the number for the 24-hr physician on-call. All participants, both those not taking and taking concurrent medications, will be monitored closely throughout the study for possible signs and symptoms of serotonin syndrome and weight loss. Participants' mental status and physical health are monitored weekly during the study period by a psychiatrist. Vital signs will be obtained at each study visit. Weight will be assessed weekly to monitor for possible excessive weight loss and used to calculate BMI. At clinic visits, a physician will assess participants for signs and symptoms of adverse effects of lorcaserin, noting which if any symptoms are present, the severity of the symptoms, make adjustments to study medication dose, discontinue study medication, or withdraw participant(s) from the study if needed. Female participants who are engaging in sexual activity with men must use adequate methods of contraception which will be discussed repeatedly during the screening process. Serum pregnancy tests will be conducted during screening and urine pregnancy tests will be performed monthly during the study. If a female participant does become pregnant or wishes to become pregnant, study medication will be immediately discontinued, she will be withdrawn from the study, and offered continuing nonpharmacological treatment (psychotherapy).

Procedures to Minimize Other Risks:

With regards to the risks of blood draws, only staff trained in phlebotomy will draw blood from participants to minimize risks of infection. Participants will be warned of the possible associated discomfort and slight bruising following blood draws. They can decline blood draws at any time. We aim to reduce the risk of using reimbursements and incentives to buy drugs such as cannabis by keeping reimbursements at a low monetary value, earned in increments of \$5. The additional monetary incentives for completion of study related activities are felt to be modest, appropriate, and limited. This payment schedule has been used successfully in treatment studies in our clinic and others with no observed effect of increased drug use. With regards to risks associated with interviews, rating scales, and questionnaires, patients are informed that they may refuse to answer any questions and may ask to stop at anytime. If participants become upset during the interviews/assessments, assistance will be made available to them.

Methods to Protect Confidentiality

Describe methods to protect confidentiality

This study has a Certificate of Confidentiality. The Certificate of Confidentiality will allow investigators and others with access to research records to refuse to disclose information that could identify subjects in any civil, criminal, administrative, legislative, or other proceeding, whether at the Federal, State, or local level. The Certificate of Confidentiality is granted for studies that collect information that, if disclosed, could damage subjects' financial standing, employability, insurability, or reputation, or have other adverse consequences.

We use coded records (i.e., initials and numbers), store signed consent forms in a locked file cabinet, and try, to the best of our ability to maintain confidentiality. Only coded records will be entered into the computer and the security of electronic data is ensured at the level of the server, the user, and the database.

Illumivu secure, encrypted servers will store anonymous data gathered through EMA. The data gathered includes self-report of substance use and impulsivity. Illumivu will not have access to any information that identifies the participant, nor will they access the de-identified data collected from the EMA unless requested by the PI. Select STARS staff can access the de-identified data using a password to access the encrypted server where the data is stored. Access to this folder is limited to necessary study personnel. Only STARS has access to de-identifiers assigned by a STARS research coordinator at the time of EMA training.

Will the study be conducted under a certificate of confidentiality?

Yes, we will apply for the Certificate of Confidentiality

Direct Benefits to Subjects

Direct Benefits to Subjects

There are no direct benefits to the participants through their enrollment in the study. There is the potential benefit of reducing cannabis use with lorcaserin treatment and, in combination with a medication compliance enhancement therapy (medical management), may lead to reduction/cessation of marijuana use. Often patients entering and remaining in treatment studies for cannabis or other substance use disorders exhibit some improvement in personal, medical and psychiatric domains whether or not the specific medication is demonstrated effective.

Compensation and/or Reimbursement

Will compensation or reimbursement for expenses be offered to subjects?

Yes

Please describe and indicate total amount and schedule of payment(s).

Include justification for compensation amounts and indicate if there are bonus payments.

For each visit participants attend, they receive \$5. Over the course of the study, they can receive up to \$130 for visit attendance. They will also receive a \$5 for each week that they bring in their medication bottle, for a maximum for \$65. They will receive \$5.50 per visit for transportation for a maximum of \$143 in transportation compensation. During the study they will complete EMA. During the 5 weeks of the study, where the phone assessments include questions on impulsivity, they can be compensated a percentage of \$20 for those 5 weeks based on a percentage of completion of the impulsivity questions, for a maximum of \$100. They can receive a total of \$438 with complete adherence to study visits and procedures.

References

References

References

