1. Lifetime history of DSM-V diagnosis of schizophrenia or schizoaffective disorder	MINI interview by therapist, Clinical interview by psychiatrist
2. Current DSM-V criteria for a psychiatric disorder supported by the MINI that in the investigator's judgment is unstable, would be disrupted by the study medication, or is likely to require new pharmacotherapy or psychotherapy during the study period. Individuals who are currently stable on psychotropic medication for at least 3 months may be included if in the investigator's opinion the psychotropic medication is compatible with the study medication (lorcaserin).	MINI interview by therapist, Clinical interview and mental status exam by psychiatrist, contact with collateral information as needed and available
3. Individuals who meet DSM-V criteria for any moderate to severe substance use disorder other than cannabis, caffeine or nicotine use disorders. (Individuals are not required to abstain from all substances and those who meet criteria for a co-occurring mild SUD can be included; though cannot meet criteria for a moderate or severe substance use disorder other than cannabis, caffeine or nicotine use disorders).	MINI interview by therapist, Clinical interview by psychiatrist
4. Pregnancy, lactation, or failure to use adequate contraceptive method in female patients who are currently engaging in sexual activity with men	Clinical interview by psychiatrist, physical examination and medical history by psychiatrist or NP, urine pregnancy test, serum HCG
5. Unstable medical conditions, such as AIDS*, cancer, uncontrolled hypertension, uncontrolled diabetes, pulmonary hypertension or heart disease	Medical history and physical examination by psychiatrist or NP, laboratory tests (serum Chem-20 and CBC, urinalysis), ECG
6. Legally mandated to participate in a substance use disorder treatment program	Participant self-report, Clinical interview by psychiatrist
7. Current or recent history of significant violent or suicidal behavior, risk for suicide or homicide	Participant self-report, Clinical interview by psychiatrist
8. Currently meets DSM-V diagnosis for an eating disorder or is underweight (BMI <18.5)	MINI interview by therapist, Clinical interview by psychiatrist
9. Elevated liver function tests (AST and ALT > 3	Laboratory tests (serum Chem-20)

times the upper limit of normal) or impaired renal function	

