- 1) Any development of serious psychiatric symptoms **or worsening of any substance use, such as alcohol or other drugs, including cannabis (see details for cannabis under "2")**, as indicated by the Clinical Global Impression (CGI) improvement score of 6 (much worse than baseline) or greater for 2 consecutive weeks will prompt a clinical evaluation and then clinical judgment as to whether the patient should be discontinued from the study, rather than a definitive discontinuation criterion. Such evaluation will be documented in the clinical chart, and based on other supportive assessments such as the C-SSRS. **Any evaluation that prompts a score of 6 or more on the CGI will be followed up by staff and discussed with the participant at his/her next clinic visit.**
- 2) A participant's continued marijuana use that ultimately places him/her at risk for self-destructive behavior

or other harm as indicated by a CGI improvement score of 6 or more (much worse than baseline) for 2 consecutive weeks will prompt a clinical evaluation and then clinical judgment as to whether the patient should be discontinued from the study, rather than a definitive discontinuation criterion. Such evaluation will be documented in the clinical chart, and based on other supportive assessments such as the C-SSRS.

Any evaluation that prompts a score of 6 or more on the CGI will be followed up by staff and discussed with the participant at his/her next clinic visit.

3) Development of serious medical condition(s) that may or may not be related to study participation (e.g., unhealthy weight loss, serotonin syndrome) as assessed by weekly visits with the psychiatrist, vital sign measurements, and weekly weigh-ins

4) If the participant becomes pregnant as assessed by monthly urine pregnancy testing

5) Weight loss resulting in the participant becoming underweight (BMI<18.5). BMI will be calculated weekly.

Blood and other Biological Samples

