Please create or insert a table describing the proposed collection of blood or other biological specimens. Blood samples (20ml) for routine analyses (ie: chemistry and hematology) will be taken at the time of medical screening. They will be repeated at 1 month following initiation of study medication and then end of study. Women will receive a serum pregnancy test at screening, followed by urine pregnancy testing every month throughout the study following initiation of medication. Quantitative urine toxicology will be collected at screening, followed by quantitative urine THC levels and creatinine twice weekly throughout the study.

Blood and Other Biological Sample(s)	Time Point(s) Collected
Blood chemistries, CBC, liver function tests	Screening, week 13
Serum pregnancy test	Screening
Urinalysis	Screening
Urine pregnancy test	Screening, week 2, 4, 9, 13
Quantitative urine toxicology and creatinine	Screening
Quantitative urine delta-9-THC and creatinine	Weekly following start of study

Assessment Instruments

Create a table or give a brief description of the instruments that will be used for assessment

Medical/Physiological Measurements

Vital Signs and Weight-5min

History and Physical Examination-30min

Electrocardiogram-15min

Pregnancy Test urine—5min

Pregnancy Test serum-5min

Urinalysis-5min

Urine testing for delta-9-THC and cannabinoids (At Screening)-5min

Quantitative urine toxicology with creatinine (weekly throughout study)-5min

Serum Laboratory Examination (CBC, Chem-7, LFTs)-5min

Interviews

Clinical Global Impressions Scale Observer (CGI-O)-5min

Timeline Follow-Back (TLFB)-10min

Hamilton Depression Scale (HAM-D)-5min

Systematic Assessment for Treatment Emergent Effects (SAFTEE)-3min

Columbia-Suicide Severity Rating Scale (C-SSRS)- 5min

Self-Reports

Fagerstrom Test for Nicotine Dependence (FTND)-5min

EMA self reporting on substance use and BIS-7-3min

-participants can self-initiate use of cannabis (log episodes of use) at any time of day through the EMA application

-Daily throughout the study, participants will receive a prompt in the evening asking about number of episodes of use of cannabis, number of cigarettes, and report of any of other substance use.

-During weeks 1, 2, 3, 4, and 13, participants will be asked to complete daily BIS-7 self-reports. The BIS (Barratt Impulsiveness Scale)-7 is an abbreviated version of the BIS-30. (Ansell, 2015)

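### Exclusion 9 joins AST and ALT with *and*, so one enzyme above 3 times the upper limit does not meet the protocol's only numeric liver rule

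*Protocol*

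**What the plan says.** Exclusion 9 in the Protocol's Inclusion/Exclusion Criteria table has a liver limb and a renal limb. The liver limb opens "Elevated liver function tests (AST and ALT > 3". The text then runs on "times the upper limit of normal) or impaired renal function", so renal impairment is a separate trigger introduced by *or*. The method of ascertainment is the screening serum chemistry panel, with no further decision rule.

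Three other places bear on liver safety, and none gives an enzyme cut-off:

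- The table under Blood and other Biological Samples schedules "Blood chemistries, CBC, liver function tests" at screening and week 13. The text above it adds routine chemistry 1 month after starting medication.
- Exclusion 5 covers "Unstable medical conditions, such as AIDS*, cancer, uncontrolled hypertension, uncontrolled diabetes, pulmonary hypertension or heart disease". It does not name liver disease.
- Criteria for Early Discontinuation includes "Development of serious medical condition(s) that may or may not be related to study participation", which is left to clinical assessment.

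**The concern.** An exclusion threshold should give the same answer whoever applies it. Here the answer depends on how one conjunction is read. Taken literally, *and* requires both enzymes to be above the limit, so a marked rise in only one leaves the candidate eligible under the protocol's only numeric liver rule.

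The section on procedures for minimizing risks says the eligibility criteria are there to protect participants by excluding people who would be at increased risk. If the threshold misses a single-enzyme elevation, that protection falls to individual judgement, and two careful staff members could decide the same case differently. What is at stake is who may receive study drug. The efficacy analysis is not involved.

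**Working it through.** No sample size, power or significance level enters this point, so there is no plan figure to reproduce. The check has four steps.

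**1. The rule as a truth table.** Inputs: the two enzymes, the connector and the threshold of 3 × ULN, all from exclusion 9.

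| AST > 3 × ULN | ALT > 3 × ULN | With *and* (as written) | With *or* |
|---|---|---|---|
| yes | yes | excluded | excluded |
| yes | no | not excluded | excluded |
| no | yes | not excluded | excluded |
| no | no | not excluded | not excluded |

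Only the two single-enzyme rows change.

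**2. A worked case (illustrative values).** ALT = 8 × ULN and AST = 2.9 × ULN. 8 > 3 is true and 2.9 > 3 is false. True *and* false is false, so the candidate is not excluded. True *or* false is true, so the candidate is excluded.

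**3. Whether the protocol uses *and* loosely for *or*.** The renal limb of the same criterion uses *or*. Exclusion 4 (pregnancy, lactation, contraception) and exclusion 8 (eating disorder, underweight) also use *or* between alternative triggers. The risk-minimization section describes the baseline work-up as designed "to detect chronic and/or unstable medical illnesses", so the author had a form available for cases where either condition is enough. This usage favors the literal reading without proving it was intended.

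**4. Planned exposure of a candidate who is admitted.** Under Medication Dosing Schedule, medication starts on Day 8, and the last dose is on the first day of week 13.

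- First day of week 13 = 12 × 7 + 1 = Day 85. By the same count week 4 starts on 3 × 7 + 1 = Day 22, which matches the protocol.
- Dosing days = 85 − 8 + 1 = 78.
- 78 / 7 = 11.1 weeks.

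This is the planned treatment period for any participant who completes, with allocation 1:1 to lorcaserin or placebo. It shows how long an admitted candidate could be dosed and does not measure harm.

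**The case against.** The strongest reply is that the words sit in a parenthesis after a plural noun, where *and* may simply list two tests that share a limit. A clinician could then exclude on either enzyme. That reading is possible, and it stands. It does not remove the problem, because the criterion then supports two opposite decisions and its ascertainment entry does not choose between them.

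The second reply is that clinical safeguards cover the case. Exclusion 5 is open-ended and its methods include "laboratory tests (serum Chem-20", so the clinician already has the chemistry panel. Each candidate's eligibility is discussed at a weekly screening meeting at a single site, which limits inconsistency. Once on study, the physician may reduce the dose, stop the drug or withdraw the participant. All of this is correct and lowers the practical risk. But these provisions permit exclusion without requiring it, and none supplies a number.

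The third reply is that nothing in the protocol shows *and* to be wrong: no hepatic risk is listed for lorcaserin, and a sponsor may require both enzymes. That also stands, and it is why the point is minor. If both are required, the criterion should say so plainly.

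Finally, screening runs under a separate protocol, #6582R, which was not available. It may set laboratory limits of its own, so the statement that this is the only numeric liver rule applies to this protocol alone.

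**Conclusion.** The concern holds, at the lowest severity. As worded, exclusion 9 is not met by a single enzyme above 3 × ULN, and nothing else in this protocol requires such a candidate to be excluded. Two of the four enzyme combinations are decided differently by *and* and *or*.

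The conclusion rests on the literal reading, which the table's own use of *or* supports, and on no overriding limit in the separate screening protocol. The number of people affected is unknown because the documents give no enzyme values. No outcome, sample size or analysis depends on the wording.

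**What to change.** In exclusion 9, replace *and* with *or* between AST and ALT, keeping the limit of 3 times the upper limit of normal and the renal limb unchanged. If the intention is that both enzymes must be raised, insert *both* before AST so that the rule has one reading.

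The cost is one word in the protocol. Under *or* there may be a few more screen failures. No new test is needed, because the serum chemistry panel is already the stated method for this criterion.
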